6.2 Missing Data

Patients with missing demographic information (including age, sex, and race) will be excluded from the study.

6.3 Significance Levels

Two-sided hypothesis testing will be applied to test statistical significance, but multiple testing adjustment for controlling type I error rates will not be applied. A p-value of <0.05 will be considered statistically significant. SAS for Windows Version 9.4 (Cary, NC) will be used for all statistical analyses.

6.4 Other Analyses**6.4.1 Outcomes Analyses**

All the analyses will be performed separately in VHA and Truven claims database.

Research Objective 1: Primary Objective 1Descriptive Analysis

All study variables including demographics, clinical characteristics, and treatment patterns of insulin (i.e., TDD, adherence, prescription fill rate, claim gaps, and concomitant medication use)

[2019-8636] Observational Study Protocol

will be analyzed descriptively before and after high-dose U-500R Kwikpen initiation, high-dose U-500R syringe initiation, and any high-dose U-500R initiation.

Numbers and percentages will be provided for dichotomous and polychotomous variables. Means and standard deviations (SDs) will be provided for continuous variables. To determine the statistical significance of before and after values, McNemar's test will be used for categorical variables, and the paired t-test will be used for continuous variables.

Multivariate Analysis

A mixed linear model will be used to evaluate factors associated with insulin adherence in the pre- and post-index periods among high-dose U-500R Kwikpen initiators, high-dose U-500R syringe initiators, and any high-dose U-500R initiators. Mixed linear models are used for studies with a longitudinal feature in which a continuous outcome variable is measured for the same subject repeatedly over the time period. Based on the distribution of the data, observations measured for the same subject are likely to be correlated over the study period, and these measurements are considered *multilevel* data. In addition, mixed linear models have a mixed effect consisting of both fixed and random effects. Time-varying and time-invariant variables can both be included in the model. In the current model, adherence (measured at 2 time intervals [before and after the index event: U-500R initiation]) will be considered the dependent variable. Observed TDD will be designated as the time varying covariate in the model (measured both before and after the index event), and the time-independent covariates will include the demographic and clinical characteristics.

The complete list of time varying and time-independent covariates will include:

- age;
- sex;
- race;
- BMI;
- Pre-index CCI score;
- observed TDD from claims; and
- time (pre/post).

Note:

- ❖ Age, sex, race, BMI, and CCI score will be assessed during pre-index period. Adherence (PDC) and observed TDD will be calculated during the entire pre-index and post-index periods, respectively.
- ❖ The abovementioned statistical approach for Primary Objective 1 will be repeated in the subgroup analyses for elderly population and other subgroup high-dose cohorts (i.e., TDD =201-300 units and TDD >300 units [optional]).

[2019-8636] Observational Study Protocol**Research Objective 2: Primary Objective 2**Descriptive Analysis

HbA1c will be analyzed descriptively before and after high-dose U-500R Kwikpen initiation, high-dose U-500R syringe initiation, and before and after any high-dose U-500R initiation.

Numbers and percentages will be provided for dichotomous and polychotomous variables. Means and SDs will be provided for continuous variables. McNemar's test will be used to determine statistical significance of before and after values for categorical variables, and the paired t-test will be used to assess the statistical significance of before and after values in continuous variables.

Multivariate Analysis: HbA1cMixed Linear Model

A mixed linear model (see details above) will be used to evaluate factors associated with HbA1c level in the pre-and post-index periods among high-dose U-500R Kwikpen initiators, high-dose U-500R syringe initiators, and any high-dose U-500R initiators. For this objective, the mixed linear model will help to evaluate the effect of both time-varying and time-independent variables on the HbA1c, while taking into account for correlation due to multiple assessments from the same individual. In the current model, HbA1c level, (measured at 2 time intervals [before and after the index event: U-500R initiation]), will be considered the dependent variable. Observed TDD will be designated as the time-varying covariate in the model (measured both before and after the index event), and the time-independent covariates include the demographic and clinical characteristics.

The complete list of covariates will include:

- age;
- sex;
- race;
- BMI;
- Pre-index CCI score;
- observed TDD from claims; and
- time (pre/post).

Note:

- ❖ Age, sex, race, BMI, and CCI score will be assessed during the pre-index period. Observed TDD will be calculated during the entire pre-and post-index periods, respectively. Pre-index HbA1c will be defined as the HbA1c measurement -90/+30 days of the index date. For patients with multiple HbA1c measurements within this period, the measurement taken closest to the index event date will be reported as the pre-index HbA1c value. Post-index HbA1c will be defined as the last HbA1c in the follow-up period.
- ❖ The abovementioned statistical approach for Primary Objective 2 will be repeated in the subgroup analyses for the elderly population and other subgroup high-dose cohorts (i.e., post-index TDD =201-300 units and post-index TDD >300 units [optional]).

[2019-8636] Observational Study Protocol**Research Objective 2: Secondary Objective 2a**Descriptive Analysis

The number of hypoglycemia events will be analyzed descriptively before and after high-dose U-500R syringe initiation, high-dose U-500R Kwikpen initiation, and before and after any high-dose U-500R initiation.

Numbers and percentages will be provided for dichotomous and polychotomous variables. Means and SDs will be provided for continuous variables. To determine the statistical significance of before and after values, McNemar's test will be used for categorical variables, and the paired t-test will be used for continuous variables.

Multivariate Analysis: Hypoglycemia Event*Zero-inflated negative binomial mixed model*

A zero-inflated negative binomial mixed model will be used to evaluate factors associated with the number of hypoglycemia events PPPY in the pre-and post-index periods among high-dose U-500R Kwikpen initiators, high-dose U-500R syringe initiators, and any high-dose U-500R initiators cohorts. Zero-inflated negative binomial distribution is a mixture of a binary distribution that is degenerate at zero and an ordinary count distribution such as a negative binomial. In cases of outcome variables being repeatedly measured from the individual subjects, zero-inflated models are extended to include random effects to account for the correlation among the repeated measures within a subject. In the current model, the number of hypoglycemia events that might have more zeroes (for example, some patients might not have a lab visit for glucose) and is measured at 2 time intervals (before and after the index event: U-500R initiation), will be considered the dependent variable. Observed TDD and HbA1c will be designated as the time-varying covariates in the model (measured both before and after the index date), and the time-independent covariates will include the demographic and clinical characteristics.

The complete list of covariates will include:

- age;
- sex;
- race;
- BMI;
- Pre-index CCI score;
- observed TDD from claims;
- HbA1c; and
- time (pre/post).

[2019-8636] Observational Study Protocol**Note:**

- ❖ Age, sex, race, BMI, and CCI score will be assessed during the pre-index period. Observed TDD and HbA1c will be calculated during the entire pre-index and post-index periods, respectively. Pre-index HbA1c will be defined as the HbA1c measurement -90/+30 days of the index date. For patients with multiple HbA1c measurements within this period, the measurement taken closest to the index event date will be reported as the pre-index HbA1c value. Post-index HbA1c will be defined as the last HbA1c in the follow-up period.
- ❖ The abovementioned statistical approach for Primary Objective 2a will be repeated in the subgroup analyses for the elderly population and other subgroup high-dose cohorts (i.e., TDD =201-300 units and TDD >300 units [optional]).

Research Objective 3: Exporatory Objective 3Descriptive Analysis

Out-of-pocket pharmacy costs will be analyzed descriptively before and after high-dose U-500R syringe initiation, high-dose U-500R Kwikpen initiation, and any high-dose U-500R initiation. Numbers and percentages will be provided for dichotomous and polychotomous variables. Means and SDs, along with the median, minimum and maximum will be provided for continuous variables. To determine the statistical significance of before and after values, McNemar's test will be used for categorical variables, and the paired t-test will be used for continuous variables.

Multivariate Analysis

A generalized linear mixed model (details above) with log link will be used to evaluate factors associated with insulin-related out-of-pocket pharmacy costs in the pre-and post-index periods among high-dose U-500R syringe initiators, high-dose U-500R Kwikpen initiators, and any high-dose U-500R initiation. For this objective, the mixed linear model will help to evaluate the effect of both time-varying and time-independent variables on the costs, while taking into account for correlation due to multiple assessments from the same individual. In the current model, costs (measured at 2 time intervals [before and after the index event; U-500R initiation]) will be designated as the dependent variable. Observed TDD will be designated as the time-varying covariate in the model (measured both before and after the index date), and the time-independent covariates will include the demographic and clinical characteristics.

The complete list of covariates will include:

- age;
- sex;
- region;
- pre-index CCI score;
- observed TDD from claims ;
- Medicare (yes/no); and
- time (pre/post).

[2019-8636] Observational Study Protocol

[figure not shown]
Note:

- ❖ Age, sex, region, Medicare (yes/no), and CCI score will be assessed during the pre-index period. Observed TDD will be calculated during both the entire pre-index and post-index periods.
- ❖ Adherence will not be included as a covariate here due to the high collinearity between time and adherence.

Exploratory Analysis: Mediator Effect of Adherence (PDC) and Observed Total Daily Dose (TDD) on Insulin-related Pharmacy Costs

Mediation analysis is a collection of methodologies designed to formalize and quantify possible mechanisms (i.e., causal pathways) linking a cause to an effect^{35,36}. The total effect of an exposure on an outcome is decomposed into direct (blue thick arrow) and indirect effects (red arrows) through mediators. Causal mediation analysis further defines both direct and indirect effects based on counterfactual models and is able to provide a causal interpretation. Causal mediation analysis is becoming an important tool for investigating pathways or mechanisms that explains the treatment effect and the underlying mechanism in epidemiology and in the social sciences.

In contrast to non-U-500R insulin therapies that are mostly basal-bolus regimen that requires more than one insulin use at a time, U-500R is an insulin-monotherapy. It is expected that, if the insulin requirement of patients and their adherence behavior were to remain the same, the out-of-pocket costs for purchasing insulins would be lower for the period when patients were exposed to U-500R treatment than for the period when patients are exposed to other insulins. However, from a previous study, it is observed that the observed total daily dose and PDC were different before and after patients were exposed to U-500R. While patients' underlying insulin requirement may or may not have changed, the changes in the observed total daily dose using claims data may reflect more of the compliance behavior (i.e. using the right amount of insulin). Similarly, PDC, another aspect of treatment compliance, may change due to the different insulin treatment characteristics. Changes in obtained insulins quantity (reflected in TDD) as well as changes in number of days with insulins (reflected in PDC) will impact number of insulin purchases (i.e. number of claims filed) and therefore the amount of out-of-pocket costs. As a result, the observed insulin-related out-of-pocket costs may be impacted by the change in the copay needed (direct effect of the exposure to different insulins) as well as the changes in TDD and PDC (indirect effect of the exposure to different insulins)

[2019-8636] Observational Study Protocol

Confounder
(age, gender, CCI, weight, HbA1c, etc.)

Mediation analysis following the below modeling steps will be considered to understand the impact of index event (time: pre-index indicates use of other non-U-500R insulins and post-index indicates exposure to U-500R use) on insulin-related out-of-pocket costs through potential mediators. Adherence (measured by PDC) and Observed Total Daily Dose (TDD) are considered as potential mediators between costs and treatment period (i.e. exposure). The key steps in mediation analysis include a model of the outcome (costs) as a function of both the mediators (PDC, and TDD) and the predictor (treatment period) and a model of the mediators (PDC and TDD) as functions of the predictor (treatment period). Confounders will be included in the models. Unfortunately, certain confounding variables are unobserved in claims data, e.g., weight, HbA1c.

- 1.) Suppose the dataset consists of n patients. For patient i ($i = 1, \dots, n$), denote by Y_{ik} the outcome variable of interest, e.g. costs, during the period k ($k = 0, 1$), where $k = 0$ refers to pre-index period and $k = 1$ refers to the post-index period.
- 2.) Let M_{ijk} be the mediators at period k , and $j=1,2$ denotes the different mediators PDC and TDD
- 3.) Let A_{ik} be a binary indicator of treatment during period k . Write $\mathbf{A}_i = \{A_{ik}\}_k$. According to the design, all the patients did not take the U-500R during the pre-index period, but they took the U-500R during the post-index period, thus $A_{ik} = k$ for $k = 0, 1$.
- 4.) A set of covariates as potential confounding variables, including age, sex, region, pre-index CCI score.

$$Y_{ik} = \beta_0 + \beta_A A_{ik} + \beta_{M1} M_{i1k} + \beta_1 \text{Age} + \beta_2 \text{Sex} + \beta_3 \text{Region} + \beta_4 \text{CCI} + \beta_5 M_{i1k} + \beta_6 M_{i2k} + d_i + \varepsilon_{ik}$$

$$M_{ijk} = \alpha_0 + \alpha_{Aj} A_{ik} + \alpha_{1j} \text{Age} + \alpha_{2j} \text{Sex} + \alpha_{3j} \text{Region} + \alpha_{4j} \text{CCI} + b_{0i} + b_{Mij} + b_{Ai} A_{ik} + \eta_{ijk},$$

where random errors ε_{ik} and η_{ijk} along with random effects d_i , b_{0i} and b_{Ai} are mutually independent over i, j, k . The random effects b_{i0} and b_{iA} capture the dependence among M_{ijk} 's. The random effects d_i 's, control the dependence between the outcome variable between the pre-index and post-index periods given the mediators and confounders,

Once the coefficient estimates from the models fitting are obtained, the mediation effects will be estimated following standard decomposition approach using counterfactual framework. The confidence intervals will be provided by using parametric bootstrap approach.

[2019-8636] Observational Study Protocol**7. Safety Evaluations****7.1. Adverse Events**

This is a non-interventional study based on secondary data use, and therefore no ICSR reporting is required. The study protocol-defined adverse events (AEs) include hypoglycaemia. Hypoglycemia events in the pre-index and post-index period will be evaluated using the ICD-9 codes from the Ginde algorithm (Appendix 1). All protocol-defined adverse events collected will be summarized in the final study report. No other AEs will be collected.

[2019-8636] Observational Study Protocol**8. Subject Consent to Release Information, Ethical Review, and Regulatory Considerations****8.1. Subject Consent to Release Information**

As this is an observational study that uses data previously collected and does not impose any form of intervention, the data has been de-identified to protect subject privacy. Therefore, a formal Consent to Release Information form is not required.

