- ❖ **Primary Objective 1:** Evaluate the patient characteristics and treatment patterns of insulin including observed TDD in claims, adherence, prescription fill rate, claim gaps, and concomitant medication use among T2DM patients before and after high-dose U-500R syringe initiation and high-dose U-500R Kwikpen initiation separately, as well as before and after any High-dose U-500R initiation
 - Characterize high-dose U-500R Kwikpen patients, syringe patients, and any high-dose U-500R initiators
 - Determine differences between treatment patterns before and after high-dose U-500R Kwikpen initiation
 - Determine differences between treatment patterns before and after high-dose U-500R syringe initiation
 - Determine differences between treatment patterns before and after any high-dose U-500R initiation
 - Determine differences between treatment patterns among elderly T2DM patients (≥ 65 years) before and after high-dose U-500R syringe initiation, high-dose U-500R Kwikpen initiation, and any high-dose U-500R initiation
 - Determine differences between treatment patterns before and after high-dose U-500R syringe initiation, high-dose U-500R Kwikpen initiation, and any high-dose U-500R initiation among T2DM patients whose TDD is 201-300 units/day in the post-index
 - Determine differences between treatment patterns before and after high-dose U-500R syringe initiation, high-dose U-500R Kwikpen initiation, and any high-dose U-500R initiation among T2DM patients whose TDD is >300 units/day in the post-index (optional)
 - Evaluate factors associated with insulin adherence among high-dose U-500R Kwikpen initiators, high-dose U-500R syringe initiators, and any high-dose U-500R initiators
 - Evaluate factors associated with insulin adherence among elderly T2DM patients (≥ 65 years) as well as among patients by dose range 201-300 units/day, >300 units/day (optional), before and after high-dose U-500R syringe initiation, high-dose U-500R Kwikpen initiation, and any high-dose U-500R initiation

Research Objective 2: Treatment Outcomes

- ❖ **Primary Objective 2:** Evaluate the HbA1c level among T2DM patients before and after high-dose U-500R syringe initiation and high-dose U-500R Kwikpen initiation separately, as well as before and after any high-dose U-500R initiation

[2019-8636] Observational Study Protocol

- Determine differences between HbA1c level before and after high-dose U-500R Kwikpen initiation

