 - Determine differences between HbA1c level before and after high-dose U-500R syringe initiation
 - Determine differences between HbA1c level before and after any high-dose U-500R initiation
 - Determine differences between HbA1c level among elderly T2DM patients (≥ 65 years) before and after high-dose U-500R syringe initiation, high-dose U-500R Kwikpen initiation, and any high-dose U-500R initiation
 - Determine differences between HbA1c level before and after high-dose U-500R syringe initiation, high-dose U-500R Kwikpen initiation, and any high-dose U-500R initiation among T2DM patients whose TDD is 201-300 units/day in the post-index
 - Determine differences between HbA1c level before and after high-dose U-500R syringe initiation, high-dose U-500R Kwikpen initiation, and any high-dose U-500R initiation among T2DM patients whose TDD is >300 units/day in the post-index (optional)
 - Evaluate factors associated with HbA1c level in the pre-and post-index periods among high-dose U-500R Kwikpen initiators, high-dose U-500R syringe initiators, and any high-dose U-500R initiators
 - Evaluate factors associated with HbA1c level in the pre-and post-index periods among elderly T2DM patients (≥ 65 years), as well as among patients by dose range 201-300 units/day, >300 units/day (optional), before and after high-dose U-500R syringe initiation, high-dose U-500R Kwikpen initiation, and any high-dose U-500R initiation
- ❖ **Secondary Objective 2a:** Evaluate the hypoglycemic events among T2DM patients before and after high-dose U-500R syringe initiation, high-dose U-500R Kwikpen initiation separately, as well as before and after any high-dose U-500R initiation
- Determine differences between hypoglycemia events before and after high-dose U-500R Kwikpen initiation
 - Determine differences between hypoglycemia events before and after high-dose U-500R syringe initiation
 - Determine differences between hypoglycemia events before and after any high-dose U-500R initiation
 - Determine differences between hypoglycemia events among elderly T2DM patients (≥ 65 years) before and after high-dose U-500R syringe initiation, high-dose U-500R Kwikpen initiation, and any high-dose U-500R initiation
 - Determine differences between hypoglycemia events before and after high-dose U-500R syringe initiation, high-dose U-500R Kwikpen initiation, and any high-dose U-500R initiation among T2DM patients whose TDD is 201-300 units/day in the post-index

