Concomitant medications ^{28,29,30}	Truven: Outpatient pharmacy claims table VHA: Pharmacy file	A flag will be created for patients prescribed the following antihyperglycemic agents (AHA):

[2019-8636] Observational Study Protocol

Variable	Source	Definition
		thiazolidinediones, sulfonylureas, biguanides, meglitinides, alpha-glucosidase inhibitors, DPP-4 inhibitors, SGLT-2 inhibitors, bile acid sequestrants, fixed-dose combinations, GLP-1 receptor agonists, and amylin agonists (Appendix 1).
HbA1c ³¹	VHA: Lab file	The HbA1c value in the pre-index and post-index period for each index event will be reported. Pre-index HbA1c will be the HbA1c measurement -90/+30 days of the index date. For patients with multiple HbA1c measurements within this period, the measurement taken closest to the index event date will be reported as the pre-index HbA1c value. The post-index HbA1c value will be the farthest HbA1c measurement taken in the time period after the 30 day-post index event date.
Change in HbA1c		The change in HbA1c will be defined as the difference in the pre-index and post-index HbA1c values.
Hypoglycemic events	Truven: Inpatient service table, outpatient service table VHA: Inpatient and outpatient files, Lab file and Pharmacy file	Hypoglycemia events in the pre- and post-index periods will be evaluated using the ICD-9 codes from the Ginde algorithm (Appendix 1), ³² the presence of a cutoff of blood glucose ≤ 70 mg/dL, or any evidence of intramuscular glucagon administration (Appendix 1). Hypoglycemia events that occurred on or after the index date will be considered the follow-up hypoglycemia event; and hypoglycemia event occurred on or prior to - 1 day of the index date will be considered as the pre-index hypoglycemia event. The number of hypoglycaemia events per patient per year (PPPY) will be reported in both the pre-and post-index periods.

[2019-8636] Observational Study Protocol

Variable	Source	Definition

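### No planned analysis of HbA1c or hypoglycemia accounts for non-insulin glucose-lowering drugs started or stopped when U-500R was initiated, so such changes can be mixed into the before/after difference

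*Protocol*

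**What the plan says.** **Capture.** Section 5.5, Table 2 records concomitant drugs by class: "A flag will be created for patients prescribed the following antihyperglycemic agents (AHA". The row gives no time window.

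**Description.** Section 4.1, Primary Objective 1 covers "treatment patterns of insulin including observed TDD in claims, adherence, prescription fill rate, claim gaps, and concomitant medication use", before and after initiation. Section 6.4.1 repeats this for the descriptive analysis ("treatment patterns of insulin (i.e., TDD, adherence, prescription fill rate, claim gaps, and concomitant medication use") and assigns the tests: "McNemar's test will be used for categorical variables, and the paired t-test will be used for continuous variables". A before/after comparison of AHA use is therefore planned.

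**HbA1c model (Section 6.4.1, Primary Objective 2).** "Observed TDD will be designated as the time-varying covariate in the model (measured both before and after the index event". The list introduced by "The complete list of covariates will include" holds age, sex, race, BMI, pre-index CCI score, observed TDD and time (pre/post).

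**Hypoglycemia model (Section 6.4.1, Secondary Objective 2a).** "Observed TDD and HbA1c will be designated as the time-varying covariates in the model (measured both before and after the index date". The list is otherwise the same.

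**Eligibility (Section 5.3.1).** Other insulins and pump use are excluded after the index date. Oral agents appear only in the rule that separates type 1 from type 2 diabetes. Stable AHA treatment is not required.

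**The concern.** The objectives are within-patient differences, for example "Determine differences between HbA1c level before and after any high-dose U-500R initiation", and Section 3 states that the study is to examine effectiveness and safety. Readers will take the pre/post difference as the result of U-500R.

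A visit at which insulin is changed is also a natural occasion to change other agents. If a glucose-lowering agent is added then, part of the HbA1c change belongs to that agent. If a sulfonylurea or meglitinide is stopped, part of any fall in hypoglycemia belongs to the stop; a start would act the other way. The planned description can show that such a shift happened, but not how much of the HbA1c or hypoglycemia change goes with it.

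Both covariate lists are declared complete, so the omission from the models is a stated choice and not a detail left open.

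**Working it through.** **1. There is no figure to reproduce.** Section 6.1 gives attrition counts only (Table 3: 647 Kwikpen and 1,766 syringe patients in VHA). The protocol has no effect size, SD or AHA start or stop rate.

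**2. Where an AHA change goes in the model.** Each patient contributes two values. Age, sex, race, BMI and CCI are fixed at their pre-index values and drop out of the within-patient difference:

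ΔHbA1c = β(time) + β(TDD) × ΔTDD + γ × ΔAHA + error.

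The model omits ΔAHA. If ΔAHA is unrelated to ΔTDD, the fitted time term estimates β(time) + γ × mean(ΔAHA). The paired t-test carries the same extra term. In the hypoglycemia model, time-varying HbA1c can absorb only the part of an AHA effect that acts through HbA1c.

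**3. Scale, with every input assumed.** Shift = net change in the share of patients on an agent × HbA1c effect of that agent.
- Low: 0.05 × 0.5 = 0.025 points
- High: 0.30 × 1.0 = 0.30 points

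Against the drop of about 0.7 cited in Section 3, this is 0.025/0.7 = 4% to 0.30/0.7 = 43%. That drop comes from an earlier Kwikpen study not limited to the high-dose cohort, so it serves only as a yardstick.

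**4. Effect on the paired test if U-500R itself did nothing.** Chance of p < 0.05 = Φ(b/SE − 1.96) + Φ(−b/SE − 1.96), with SE = SD/√N. Take b = 0.20 × 0.75 = 0.15 and an assumed SD of change of 1.5.
- N = 647: SE = 1.5/√647 = 0.059, b/SE = 2.54, chance 72%
- N = 1,766: SE = 1.5/√1,766 = 0.036, b/SE = 4.20, chance 99%

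Over the whole range in step 3, with SD 1.2 to 2.0, the chance runs from about 6% to above 99% at N = 647. The protocol cannot narrow this.

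**5. Would an AHA term in the main model solve it?** Only if AHA starts are unrelated to response. The simulations below use assumed inputs.

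| Setting | Estimate | Mean HbA1c change |
|---|---|---|
| True effect −0.50, AHA effect −0.75, 20% start, N = 647 | Unadjusted | −0.65 |
| Same, starts at random | Whole-period AHA term | −0.50 |
| Same, poor responders start more often (log-odds 0.5, 1, 2 per HbA1c point) | Whole-period AHA term | −0.63, −0.73, −0.82 |
| True effect −0.50, 10% start at the switch, poor responders start drugs | Unadjusted | −0.61 to −0.63 |
| Same | Only patients with unchanged classes throughout | −0.63 to −0.79 |
| Same | Keyed to changes around the index date | −0.54 to −0.56 |

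The unadjusted −0.65 follows by hand: −0.50 + 0.20 × (−0.75). When later starts respond to poor control, conditioning on whole-period AHA use can leave the estimate further from the truth than no adjustment. Conditioning on changes near the index date avoids most of that. Only the ordering should be taken from this table.

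**The case against.** **AHA use is not ignored.** It is described before and after initiation, and this is repeated in the elderly and dose subgroups. A reader might infer that AHA use is merely flagged; Sections 4.1 and 6.4.1 do not support that. The objection stands, but a description does not separate the drugs' contribution to the outcome.

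**The models are not worded causally.** They evaluate factors associated with the outcome, and counterfactual language appears only in the cost mediation analysis. A reader might infer that AHA effects are necessarily credited to U-500R. The text supports only that they can be mixed in, although the effectiveness aim in Section 3 makes the causal reading likely.

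**The covariate set has a precedent.** The earlier study cited in Section 3 adjusted for age, gender, race, BMI, CCI and TDD. Keeping that set allows the studies in the series to be read side by side. This stands, and is a reason to leave the main models alone.

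**Post-index AHA use can respond to outcome.** This also stands (step 5). An any-fill flag would, in addition, count drugs started after the last HbA1c.

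**A sensitivity analysis may be in the SAP.** The SAP is not at hand, so the absence of one from the protocol is not in itself an error. What the protocol does fix is two covariate lists called complete, with no AHA term.

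**Conclusion.** The point holds as a low-cost improvement. The HbA1c and hypoglycemia models and the paired comparisons carry no AHA information, eligibility does not require stable AHA treatment, and there is no comparator cohort. A class started or stopped at the switch therefore falls mainly into the time (pre/post) term.

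Size and direction are unknown. The 0.025 to 0.30 point range rests wholly on assumed uptake and drug effect. It is not an estimate of bias in this study, and net stopping would reverse it. A reader might infer that U-500R will look more effective or safer than it is; the protocol gives no rates that would support either direction.

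A reader might also conclude that period-specific AHA terms belong in the main models. That does not follow, because later AHA changes may be a consequence of control after the switch.

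**What to change.** 1. Keep the planned models and paired comparisons as the main result. Label them as the change with U-500R plus any concurrent AHA change.
2. In Table 2, define AHA class use separately for the pre-index period and for a short window around the index date, for example up to the 30-day post-index mark already used for HbA1c. State how a start and a stop are recognized from fills and days' supply.
3. Pre-specify a sensitivity analysis for HbA1c and hypoglycemia that adds indicators for class starts and stops in that window, or is restricted to patients with no class change in it, or both. Report it beside the main result.
4. Do not use whole-period post-index AHA flags as main-model covariates.

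The cost is programming, since the pharmacy data and class lists are already part of the plan. The restricted sample will be smaller, and AHA changes after the window remain unadjusted; the report should say so.
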